13 PHOTOGRAPHY

Standardized photography of facial acne at Baseline, and at the Weeks 2, 4, 8 and 12/End of Treatment Visit will be performed at select sites. These photographs will be optional for Patients at the selected sites and will not be used for efficacy assessment purposes. Participating Investigators shall refer to separate photographic manual for instructions.

14 SAFETY EVALUATIONS

Safety will be assessed by monitoring incidence of Cutaneous Reactions Assessments, Local Tolerability Assessments, and AEs reporting; at Baseline, at all treatment visits and end-of-treatment visit.

14.1 Cutaneous Reactions Assessments

The evaluator will assess local application site cutaneous reactions by rating the erythema, dryness, pigmentation and scaling at each study visits except Screening visit. The evaluator will determine the score for each of these variables by direct evaluation. The following definitions of terms will be applied to these evaluations.

Cutaneous Signs Evaluation will include assessments of erythema, scaling, dryness and pigmentation based on the following 4-point scale shown in table 3 below.

Table 3: Assessments of erythema, scaling, dryness and pigmentation

	Score	Rating	Definition
Erythema	0	None	No erythema
	1	Mild	Slight pinkness present
	2	Moderate	Definite redness, easily recognized
	3	Severe	Intense redness
Scaling	0	None	No scaling
	1	Mild	Barely perceptible shedding, noticeable only on light scratching or rubbing
	2	Moderate	Obvious but not profuse shedding
	3	Severe	Heavy scale production
Pigmentation	0	None	No disturbance of pigmentation
	1	Mild	Barely perceptible pigment change
	2	Moderate	Markedly darker or lighter
	3	Severe	Complete de-pigmentation or severe hyperpigmentation
Dryness	0	None	No dryness
	1	Mild	Slight but define roughness
	2	Moderate	Moderate roughness
	3	Severe	Marked roughness

Application site reactions (erythema, scaling, dryness and pigmentation) are not to be recorded as AEs unless they result in either:

- The temporary discontinuation of the study product.
- The discontinuation of the Patient from the study.
- The use of a new concomitant medication in order to treat this event.

14.2 Local Tolerability Assessments

The evaluator will assess local application site tolerability by rating the itching, burning and stinging at each study visits except Screening visit. The evaluator will determine the score for each of these variables by asking the patient to grade their experience **over the past 24 hours**. The following definitions of terms will be applied to these evaluations:

Local Tolerability Assessment: The evaluations of itching, burning and stinging will be made by the Investigator at the time of the visit.

Table 4: Assessments of Itching, Burning and Stinging

	Score	Rating	Definition
Itching	0	None	No itching
	1	Mild	Slight itching, not really bothersome
	2	Moderate	Definite itching that is somewhat bothersome
	3	Severe	Intense itching that may interrupt daily activities and/or sleep
Burning	0	None	No burning
	1	Mild	Slight burning sensation; not really bothersome
	2	Moderate	Definite warm, burning sensation that is somewhat bothersome
	3	Severe	Hot burning sensation that causes definite

			discomfort and may interrupt daily activities or sleep
Stinging	0	None	No stinging
	1	Mild	Slight stinging sensation; not really bothersome
	2	Moderate	Definite stinging sensation that is somewhat bothersome
	3	Severe	Severe stinging sensation that causes definite discomfort and may interrupt daily activities or sleep

Application site reactions (itching, burning and stinging) are not to be recorded as AEs unless they result in either:

- The temporary discontinuation of the study product.
- The discontinuation of the Patient from the study.
- The use of a new concomitant medication in order to treat this event.

Any other application site reaction not listed above should be recorded as AEs in the source document and eCRFs.

15 ADVERSE EVENTS

When an AE occurs requiring an early termination from the study for a Patient, the Investigator or medical professional in attendance will contact the Medical Monitor or the Sponsor by telephone and follow up with a written description as soon as possible. The overseeing IRB should also be notified.

15.1 Definitions

An AE is defined as any untoward medical occurrence in a Patient administered a medicinal product and which does not necessarily have to have a causal relationship with this treatment. An AE can therefore be any unfavorable and unintended sign, symptom, or disease temporally associated with the use of a medicinal product, whether or not considered related to this medicinal product.

A SAE is an AE that results in any of the following outcomes:

- Death
- Life-threatening event (i.e., the Patient was, in the opinion of the Investigator, at immediate risk of death from the event as it occurred. It does not include an event that, had it occurred in a more severe form, might have caused death
- Requires in-Patient hospitalization or prolongs hospitalization
- A persistent or significant disability/incapacity or substantial disruption of the ability to conduct normal life functions
- Congenital anomaly/birth defect
- Other AEs that may be considered serious based upon appropriate medical judgment, may jeopardize the Patient and may require medical or surgical intervention to prevent one of the outcomes listed above.

Immediately Reportable AEs (IRAE) is any SAE or any AE that necessitates discontinuation of study product, including pregnancy.

Unexpected AE is any adverse drug experience, the specificity or severity of which is not consistent with the current approved product labeling (package insert) for the study

product, the Investigator's Brochure, or as described in the clinical protocol and consent materials.

Intensity

Intensity of AEs is the maximum intensity of an AE during a day should be recorded on the eCRF. If the intensity of an AE changes over a number of days, then separate entries should be made having distinct onset dates for the changes in severity.

- Mild - AEs are usually transient, requiring no special treatment, and do not interfere with Patient's daily activities.
- Moderate - AEs typically introduce a low level of inconvenience or concern to the Patient and may interfere with daily activities but are usually ameliorated by simple therapeutic measures.
- Severe - AEs interrupt a Patient's usual daily activity and traditionally require systemic drug therapy or other treatment.

Causal Relationship to Study product

The following criteria should be used in assessing the apparent causal relationship of an AE to study product:

Definitely - The AE:

- follows a reasonable temporal sequence from study product administration
- abates upon discontinuation of the study product (de-challenge)
- is confirmed by reappearance of the reaction on repeat exposure.

Probably - The AE:

- follows a reasonable temporal sequence from study product administration
- abates upon discontinuation of the study product (de-challenge).
- cannot be reasonably explained by the known characteristics of the Patient's state.

Possible - The AE:

- follows a reasonable temporal sequence from study product administration
- but that could readily be produced by a number of other factors.

Unlikely - The AE:

- Does not follow a reasonable temporal sequence from the time of study drug administration; and
- Was likely produced by other factors such as the subject's clinical state, therapeutic intervention, or concomitant therapy but for which relationship cannot be definitely ruled out.

Not related - The AE:

- does not have a reasonable temporal association with the administration of study product
- has some other obvious explanation for the event.

Action Taken with Study Treatment

The Investigator will describe the action taken with the study treatment in the appropriate section of the eCRF, as follows:

- Dose Increased
- Dose Not Changed
- Dose Reduced
- Drug Interrupted
- Drug Withdrawn
- Not Applicable
- Unknown

Action Taken to Treat Event

The Investigator will describe other action(s) taken in the appropriate section of the eCRF, as follows:

- None
- Concomitant Medication
- Procedure/Therapy
- Hospitalization/Prolonged Hospitalization
- Withdrawal from Study
- Other

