12.10 Study Flow Chart

Procedures	Visit 1 ¹	Visit 2 ²	Visit 3 ²	Visit 4 ²	Visit 5 ²	Visit 6 ³ (EOS ⁴ / ET ⁵)
Name of Visit	Screening	Baseline Day 1	Week 2 Day 15	Week 4 Day 29	Week 8 Day 57	Week 12 Day 85
Visit Window	Day -35 to Day 0		±3 days	±3 days	±3 days	±4 days
Informed Consent/Assent	X					
Demographics	X					
Medical History/ Previous Therapies	X	X				
Brief Physical Examination & Vital signs		X				X
Inclusion/Exclusion Criteria	X	X				
Urine Pregnancy Test ⁶	X	X ⁷	X	X	X	X
Complete PRE-FACE and PGI-S ⁸	X	X	X	X	X	X
Complete PGI-C, PGI-TS and PGI-SE ⁹			X	X	X	X
Complete Acne-QoL questionnaire ¹⁰		X				X
IGA	X	X	X	X	X	X
Lesion Counts	X	X	X	X	X	X
Assessment of Eligibility		X				
Randomization		X				
Cutaneous Safety Assessment and Local Tolerability Assessments		X	X	X	X	X
Administer/ Review Patient Instructions		X	X	X	X	
Weigh Study Product		X		X	X	X
Dispense Study Product		X ¹¹		X	X	
Dispense Cleanser & Moisturizer		X ¹²				
Diary Card dispensed		X		X	X	
Study Product collected				X	X	X
Diary Card collected				X	X	X
Patient Compliance Reviewed (Diary)			X	X	X	X
Prior and Concomitant Therapy and Medication Reviewed	X	X	X	X	X	X
Assessment of Adverse Events	X ¹³	X	X	X	X	X
Photography (select site(s))		X	X	X	X	X

¹ If no washout is needed, Visits 1 and 2 may occur on the same day. If a washout is needed, visit 2 must occur within 35 days of Visit 1.

² All visit dates are in reference to Baseline, e.g., Visit 5 occurs 8 weeks ± 3 days after Baseline Visit.

³ Week 12/ End of Study procedures should be completed for Patients who terminate early.

⁴ EOS – End of Study

⁵ ET – Early Termination

⁶ All females of child-bearing potential and premenarchal must undergo Urine Pregnancy Tests, at every visit.

⁷ Urine Pregnancy test should be repeated if more than 2 weeks washout is needed.

⁸ Questionnaires are to be completed by all patients prior to any treatment related assessments. In case Screening Visit and Baseline occur at the same day, the PRO questionnaires should be completed prior to screening procedures.

⁹ Questionnaires are to be completed by all patients prior to any treatment related assessments.

¹⁰ Questionnaires are to be completed by all patients prior to any treatment related assessments. In case Screening Visit and Baseline occur at the same day, the QoL questionnaires should be completed prior to screening procedures.

¹¹ Dispense one pump of study product at the Baseline Visit and dispense additional pump at Visit 4 and 5.

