15.2 Eliciting and Reporting of Adverse Events

The Investigator will periodically assess Patients for the occurrence of AEs. In order to avoid bias in eliciting AE, the Patient or parent/legally authorized representative should be asked a non-specific question (e.g., “How have you been feeling since your last visit?”) to assess whether any AE has been experienced since the last visit. All AEs (as defined in Section 18.6), either observed by the Investigator or one of his/her medical collaborators, or reported by the Patient spontaneously, or in response to direct questioning, will be reported and documented in the source and the study reporting forms. When reporting an AE, the Investigator must assign a severity grade to each event and declare an opinion on the relatedness of the event to the study product or procedure. Serious or unexpected AEs must be reported to the CRO within 24 hours of when the Investigator first learns of the occurrence of the event.

AEs will be documented in the source document and recorded in a timely manner on eCRFs. AEs that are identified at the last assessment visit (or the Early Termination Visit) must be recorded on the AE eCRF with the status of the AE noted.

AEs reporting begins from the signing of informed consent/assent. Study product-related AEs should be followed until resolved or 30 days after the final study treatment. Regardless the duration of the study, all patients that exhibit SAE, will be followed up until the SAE resolves, based on Investigator’s medical judgment or are considered to be chronic (stabilized for at least 30 days). All events that are ongoing at this time will be recorded as ongoing on the eCRF.

The following data should be documented for each AE:

- Description of the symptom event

- Classification of “serious” or “not serious”
- Severity
- Date of first occurrence and date of resolution (if applicable)
- Action(s) taken
- Causal relationship
- Outcome of event (Recovered/Resolved, Recovered/Resolved with Sequelae, Not Recovered/Not Resolved, Unknown, Fatal [with date and cause reported])

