8.8.2 Adverse Events (AEs)

All AEs occurring during the study will be recorded and classified on the basis of MedDRA terminology. Descriptions of AEs will include the date of onset, the date the AE ended, the severity of the AE, the relationship to study product, the action taken regarding study product usage, the action taken to treat the AE, and the outcome. All reported TEAEs will be summarized by the number of patients reporting AEs, system organ class, severity, seriousness, and relationship to study product. TEAEs are those AEs with an onset on or after the date of the first study product application; if the AE is not indicated as prior to first application on the CRF then it will be considered a TEAE.

AEs will be summarized by treatment group and severity. Each patient will be counted only once within a system organ class or a preferred term by using the AEs with the highest severity within each category.

AEs will be summarized by treatment group and relationship to study product. Each patient will be counted only once within a system organ class or a preferred term by using the AEs with the greatest relationship within each category.

If relationship to study drug is reported as definitely, probably, or possible, then this is defined as related. If relationship to study drug is reported as unlikely or not related, then this is defined as unrelated.

Comparisons among treatment groups will be made by tabulating the frequency of patients with one or more AEs (classified into MedDRA terms) during the study. The Fisher's Exact test will

be used to compare the proportion of patients in each treatment group who report any AE at a significance level of 0.05. The specific system organ classes and preferred terms analyzed will be those that are reported by at least one percent of the patients in any treatment group.

All information pertaining to AEs noted during the study will be listed by patient, detailing verbatim given by the investigator, preferred term, system organ class, start date, stop date, severity, actions taken, and drug relatedness. The AE onset will also be shown relative (in number of days) to the day of initial application of the randomized study product.

Serious adverse events (SAEs) will be tabulated by patient within treatment groups.

In addition, a list of patients who discontinued from the study and a list of patients who experienced SAEs will also be provided.

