(Page 13 of 14)

Stinging	E-BPO/E-ATRA 3%/0.1% Cream (N=xxx)	Vehicle Cream (N=xxx)
Baseline		
n	xx	xx
0 – None	xx (xx.x%)	xx (xx.x%)
1 – Mild	xx (xx.x%)	xx (xx.x%)
2 – Moderate	xx (xx.x%)	xx (xx.x%)
3 – Severe	xx (xx.x%)	xx (xx.x%)
Week 2		
n	xx	xx
0 – None	xx (xx.x%)	xx (xx.x%)
1 – Mild	xx (xx.x%)	xx (xx.x%)
2 – Moderate	xx (xx.x%)	xx (xx.x%)
3 – Severe	xx (xx.x%)	xx (xx.x%)
Week 4		
n	xx	xx
0 – None	xx (xx.x%)	xx (xx.x%)
1 – Mild	xx (xx.x%)	xx (xx.x%)
2 – Moderate	xx (xx.x%)	xx (xx.x%)
3 – Severe	xx (xx.x%)	xx (xx.x%)

Note: No imputation of missing data.

SOURCE: USERNAME\SPONSOR\PROJECT\JOBNAME (DATE,TIME)

Table 14.3.1.1: Summary of Cutaneous Signs and Local Tolerability at Each Evaluation
(Safety Population)
(Page 14 of 14)

Stinging	E-BPO/E-ATRA 3%/0.1% Cream (N=xxx)	Vehicle Cream (N=xxx)
Week 8		
n	xx	xx
0 – None	xx (xx.x%)	xx (xx.x%)
1 – Mild	xx (xx.x%)	xx (xx.x%)
2 – Moderate	xx (xx.x%)	xx (xx.x%)
3 – Severe	xx (xx.x%)	xx (xx.x%)
Week 12		
n	xx	xx
0 – None	xx (xx.x%)	xx (xx.x%)
1 – Mild	xx (xx.x%)	xx (xx.x%)
2 – Moderate	xx (xx.x%)	xx (xx.x%)
3 – Severe	xx (xx.x%)	xx (xx.x%)

Note: No imputation of missing data.

SOURCE: USERNAME\SPONSOR\PROJECT\JOBNAME (DATE,TIME)

Table 14.3.1.2.1: Summary of Treatment-Emergent Adverse Event Characteristics
(Safety Population)
(Page 1 of 2)

	E-BPO/E-ATRA 3%/0.1% Cream (N=xxx)	Vehicle Cream (N=xxx)
Subjects Reporting Any Treatment-Emergent Adverse Event	xx (xx.x%)	xx (xx.x%)
Number of Treatment-Emergent Adverse Events	xx	xx
Subjects Reporting Any Serious Treatment-Emergent Adverse Event	xx (xx.x%)	xx (xx.x%)
Number of Serious Treatment-Emergent Adverse Events	xx	xx
Subjects Reporting Treatment-Emergent Adverse Event with Outcome of Fatal	xx (xx.x%)	xx (xx.x%)
Number of Treatment-Emergent Adverse Events with Outcome of Fatal	xx	xx
Subjects Who Discontinued Study Drug Due to a Treatment-Emergent Adverse Event	xx (xx.x%)	xx (xx.x%)
Number of Treatment-Emergent Adverse Events Leading to Discontinuation of Study Drug	xx	xx
Subjects Who Discontinued from the Study Due to a Treatment-Emergent Adverse Event	xx (xx.x%)	xx (xx.x%)
Number of Treatment-Emergent Adverse Events Leading to Discontinuation of Study	xx	xx

Note: Treatment-emergent adverse events are those events that were not indicated as occurring prior to first application.
Related defined as “Definitely”, “Probably”, or “Possible”. Not Related defined as “Unlikely” or “Not related”.

SOURCE: USERNAME\SPONSOR\PROJECT\JOBNAME (DATE, TIME)

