¹ Day is calculated as date - date of first application for dates prior to first application. Otherwise, day is calculated as date - date of first application + 1 for dates on or after first application.

Note: System Organ Class and Preferred Term map to MedDRA (Version 21.0).

SOURCE: USERNAME\SPONSOR\PROJECT\JOBNAME (DATE, TIME)

Listing sorted by Subject, Start Date, End Date, Adverse Event.

Listing 16.2.7.2.4: Serious Adverse Events
Treatment Arm
(Page xx of yy)

	S: MedDRA System Organ Class			
	P: MedDRA Preferred Term	A: In the Application Area		
S: Subject	A: Adverse Event	G: Severity	A: Action Taken with Study Drug	
A: Age/Sex	O: Occurred Prior to First Application	R: Relationship to Study Drug	T: Action Taken to Treat Event	S: Start Date (Day) ¹
E: Eval		S: Serious Event	O: Outcome	E: End Date (Day) ¹

S: xxxxxx	S: xxxx xxx xxxxxxxxxxxxxx xxxxxx	A: xx	A: xxx xx xxxxxxxx	S: xxxxxxxxxxxxxxxxx
A: xxxx	P: xxx xxxxxxxxxxxxxx	G: xxxx	T: xxxx	E: xxxxxxxxxxxxxxxxx
E: xxxxxxxx	A: xxxxxxxx xxx xxxxxxxxxxx xxxxx	R: xxx xxxxxxxx	O: xxxxxxxxxxxxxxxxx	
	O: xx	S: xxx		
	S: xxxxxxxx xxxxxxxxxxx xxx xxxxxxxxxxx	A: xxx	A: xxx xxxxxxxxxxx	S: xxxxxxxxxxxxxxxxx
	P: xxxxxxxxxxxxxx	G: xxxx	T: xxxxxxxxxxxxxx xxxxxxxxxxx	E: xxxxxxxxxxxxxxxxx
	A: xxxxxxxx xxx xxxxxxxxxxx xxxxx	R: xxx xxxxxxxx	O: xxxxxxxxxxxxxxxxx	
	O: xx	S: xxx		
S: xxxxxx	S: xxxx xxxxxxxxxxxxxx xxxxxx	A: xx	A: xxx xx xxxxxxxx	S: xxxxxxxxxxxxxxxxx
A: xxxx	P: xxxxxxxxxxxxxx	G: xxxxxxxx	T: xxxx	E: xxxxxxxxxxxxxxxxx
E: xxxxxxxx	A: xxxxxxxxxxx xxxxx	R: xxxxxxxx	O: xxxxxxxxxxxxxxxxx	
	O: xx	S: xxx		

¹ Day is calculated as date - date of first application for dates prior to first application. Otherwise, day is calculated as date - date of first application + 1 for dates on or after first application.

Note: System Organ Class and Preferred Term map to MedDRA (Version 21.0).

SOURCE: USERNAME\SPONSOR\PROJECT\JOBNAME (DATE, TIME)

Listing sorted by Subject, Start Date, End Date, Adverse Event.

Listing 16.2.7.2.5: Subjects Who Prematurely Discontinued Study and/or Discontinued Study Drug Due to Adverse Events
Treatment Arm
(Page xx of yy)

S: Subject	A: Age/Sex	E: Eval	S: MedDRA System Organ Class	P: MedDRA Preferred Term	A: Adverse Event	O: Occurred Prior to First Application	A: In the Application Area	G: Severity	R: Relationship to Study Drug	S: Serious Event	A: Action Taken with Study Drug	T: Action Taken to Treat Event	O: Outcome	S: Start Date (Day) ¹	E: End Date (Day) ¹

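### Splitting an AE at every intensity change inflates the TEAE event count and, by default, makes an improving pre-treatment AE treatment-emergent

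*Protocol*

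**What the plan says.** **Recording.** Under Intensity, Protocol 15.1 tells sites that if an AE's intensity changes over a number of days, "separate entries should be made having distinct onset dates for the changes in severity". It does not distinguish worsening from easing. Collection starts before treatment: "AEs reporting begins from the signing of informed consent/assent" (Protocol 15.2). Screening can last up to 35 days, or no time at all: "If no washout is needed, Visits 1 and 2 may occur on the same day" (Protocol 12.10, first footnote).

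**Definition of a TEAE.** There are three versions.
- Protocol 17.6 uses onset date only.
- SAP 8.8.2 repeats the onset rule, "TEAEs are those AEs with an onset on or after the date of the first study product application", and adds a CRF indicator: "if the AE is not indicated as prior to first application on the CRF then it will be considered a TEAE".
- The footnotes to the SAP's TEAE tables use the indicator only: "Treatment-emergent adverse events are those events that were not indicated as occurring prior to first application". The field itself appears in Listing 16.2.7.2.4 as "O: Occurred Prior to First Application".

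None of them says what happens when a pre-treatment AE continues past first application at a changed intensity.

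**Counting.** SAP 8.8.2 counts a patient at most once per SOC and once per PT, and its Fisher tests compare patients. Table 14.3.1.2.1 also reports numbers of events: all TEAEs ("Number of Treatment-Emergent Adverse Events"), then serious, fatal, and leading to discontinuation of drug or of study. Table 14.3.1.3.1 does the same for serious TEAEs. No step in either document joins the records that belong to one AE.

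**The concern.** The recording rule turns one clinical episode into several database records, each with its own onset date. The analysis rules then treat each record as an AE in its own right. A row that claims to count events therefore also counts how often intensity was re-graded. A patient whose AE began before any exposure, and then got better, can appear as having a treatment-emergent event.

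Safety is one of the two primary objectives (Protocol 7), and these tables are how it will be reported. The efficacy analyses are not touched.

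**Working it through.** The documents state no figure that could be reproduced here. The check traces the rules through simple cases.

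**1. Event-count row.** An AE with k intensity changes yields 1 + k records. For a post-dose AE running mild, moderate, mild, k = 2, so there are 1 + 2 = 3 records. The event row shows 3, while the by-patient row beside it shows 1.

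Over all AEs, let q be the share that change intensity and m the mean number of changes among those. The row is then inflated by 1 + q × m. The documents give neither quantity. Over an assumed range:
- q = 10%, m = 1: 1 + 0.10 × 1 = 1.1
- q = 50%, m = 2: 1 + 0.50 × 2 = 2.0

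**2. Serious, fatal and discontinuation event rows.** Protocol 15.2 has seriousness, severity and action taken documented for each AE. These rows count the records that carry the attribute. They are inflated only where a site repeats the attribute on more than one record of the same AE, and nothing requires that.

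**3. Patient-level tables and Fisher tests.** A patient counts once per SOC and once per PT, so splitting a post-dose AE adds 0 patients.

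**4. Pre-treatment AE still ongoing at first application.** The post-dose record is classified as follows:

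| Post-dose record | Protocol 17.6 | SAP 8.8.2, not marked prior | SAP table footnotes, marked prior |
|---|---|---|---|
| Moderate before dosing, mild after | TEAE | TEAE | not a TEAE |
| Mild before dosing, moderate after | TEAE | TEAE | not a TEAE |

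In the unmarked columns the first line is a false TEAE and the second is reasonable. If the site marks the record as prior, the footnotes exclude both, although the onset sentence in SAP 8.8.2 read alone would still include both. The outcome depends on how the site fills in a field for which the protocol and SAP give no instruction. The default, when the field is not marked, is TEAE.

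Each false TEAE adds at most one patient per SOC and PT. It needs an AE that starts between consent and first application, is still ongoing at dosing, improves afterwards, and has an unmarked second record.

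**5. With the fix.** The mild, moderate, mild case becomes 1 event in 1 patient. The moderate-to-mild pre-treatment case becomes 0 events in 0 patients. The mild-to-moderate pre-treatment case stays a TEAE.

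**The case against.** The strongest reply has four parts.

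- **The SAP does not rely on onset date alone.** It supersedes the protocol where they differ (SAP 2) and brings in a CRF indicator, and the table footnotes use nothing else. This stands: reclassification of an improving AE is conditional, not certain. It does not remove the problem. The unmarked record is a TEAE by default, and a site that follows Protocol 15.1 has just given that record a post-dose onset. Protocol 15.2 also asks for the date of first occurrence of each AE, which fits poorly with a new onset date per intensity change, so sites may differ.
- **The pre-treatment window is short and may be zero, and randomisation balances pre-dose AEs in expectation.** This stands. It limits the size, and no material shift in a Fisher comparison has been shown.
- **Nothing is tested on event counts.** This stands. The rows are descriptive and each sits beside a by-patient row.
- **Many fluctuating local reactions never become AEs.** Protocol 14.1 and 14.2 make the seven graded signs and symptoms AEs only if they lead to interruption, discontinuation from the study or new medication. This stands as a limit on volume. The reactions that do qualify are ones whose intensity may well have changed, and other application-site reactions are always AEs.

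A reader might go further and infer that the active-to-vehicle event ratio is overstated. If 30% of active-arm AEs and 10% of vehicle AEs changed grade once, the factor would be 1.30 / 1.10 = 1.18. Those shares are invented, equal shares leave the ratio unchanged, and the SAP never computes or tests such a ratio. The documents do not support a stated bias between arms.

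**Conclusion.** The concern holds in limited form. As written, the plan over-counts a continuous AE in the all-TEAE event row, once for each record of changed intensity. By default it also classifies as treatment-emergent a pre-treatment AE that eases after dosing.

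Three stronger readings are not supported. Multiple counting does not reach the SOC, PT, severity or relationship tables or the Fisher tests. The serious, fatal and discontinuation event rows do not inflate automatically. An improving pre-treatment AE does not always become a TEAE, because a site may mark its later record as prior.

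The size cannot be fixed from the documents. The factor of 1.1 to 2.0 for the event row rests wholly on assumed shares and numbers of grade changes. The second error can add patients to TEAE incidence only for AEs that began in the 0 to 35 days before first application. It is still worth correcting: a stated recording rule combined with a stated TEAE rule produces wrong reported safety numbers, and the remedy is cheap.

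**What to change.** Amend SAP 8.8.2 before unblinding, which SAP 2 allows:

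1. A record that continues a pre-dose AE at the same or lower intensity is not a TEAE. A record whose intensity exceeds the pre-dose intensity is.
2. Before filling the event-count rows of Tables 14.3.1.2.1 and 14.3.1.3.1, collapse contiguous records of the same preferred term in the same subject into one event at maximum intensity.
3. State whether onset date or the CRF indicator governs when they disagree, and bring the table footnotes into line.

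If the eCRF can still be changed, a common event number on split records would make the linking exact. Otherwise preferred term and contiguous dates will serve.

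The cost is SAP wording and a short programming step. The downside is that a true recurrence starting just as the previous episode ends would be merged with it.
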